## Hypothesis:

We hypothesize that a 'soft' cervix as indicated by shear wave elastography is positively associated with the risk of preterm birth in twin pregnancies.

### **Design of study**

This is a prospective non-interventional observational study.

## Methods

Chinese women carrying multiple pregnancies attending antenatal visit at Prince of Wales Hospital are invited to join the study. The study details will be explained by the research assistant or one of the investigators and informed consent will be obtained. Demographic data, antenatal history will be obtained. Exclusion criteria include an age of less than 18 years, non-Chinese, inability to provide consent and those who refuse to join.

Other risk factors of preterm delivery will also be documented:

- known cervical insufficiency
- surgical cerclage or pessary in previous pregnancy

• history of preterm prelabour rupture of membranes (PPROM) or spontaneous preterm birth before 34 weeks

• history of cervical surgery including cone biopsy, loop electrosurgical excision procedure, cervical tear repair, etc

- short cervix <2.5cm cervical length
- painless cervical os dilatation

A trained researcher or an obstetrician will perform transvaginal scan for the cervix on the same day of the antenatal visit, or on a separate study date, if necessary. Measurements will be done at 5 visits: 11-15 weeks, 16-19 weeks, 20-23 weeks, 24-27 weeks, 28-32 weeks. The number of visits will be depended on when the subjects are initially recruited.

The following will be measured:

- Cervical consistency by sonoelastogrpahy
- Cervical length by 2D ultrasonography
- Posterior cervical angle by 2D ultrasonography
- Fetal viability

The TVS measurement of the cervical length, posterior angle and sonoelastography is elaborated as follow:

• An USG machine equipped with shear wave elastography (SWE) is used (scale set to 0-100kPa)

• Participants are asked to empty the urinary bladder before TVS, and lie in lithotomy position

• A 12-3MHz transvaginal transducer (with double condom cover and lubricant) is inserted into the vagina gently, with no pressure exerted on the cervix

• The mid-sagittal view of the cervix is obtained and magnified

• The cervical length and the posterior angle are then measured as described in our previous study [32, 33]

• SWE mode is then switched on and a color box showing the elastogram is demonstrated

• The color box will be placed at the central part of the anterior lip of the cervix (more proximal to the USG probe than the posterior lip)

• Once the color box is uniformly filled with color signals on the elastogram, the image is frozen and a region of interest (Q-box) of size 10mm is placed to measure the tissue elasticity (in term of kPa).

• Women will be asked to perform Valsalva maneuvers and mesurements of cervical

length, posterior angle and elastography will be obtained under such maneuver.

• The acquisition time is kept short within ten seconds to avoid erroneous data collection.

• Images will be saved for future analyses, if necessary.

Women, including those who are found to have a short cervix, will be managed according to the departmental protocol and their obstetric management will not be affected by the study. The obstetrician will be blinded to the finding of the sonoelastography and the finding would not affect the obstetric management of the women.

The delivery data and neonatal outcome will be collected from the medical notes and hospital electronic system before the women are discharged after their delivery.

### Main outcome measures:

1. The association of cervical consistency in mid trimester with spontaneous preterm birth in women carrying multiple pregnancies.

2. The change in cervical consistency during pregnancy in women carrying multiple pregnancies.

### Sample Size:

The risk of preterm birth <34 weeks in twin pregnancies is approximately 20%. A sample size of 120 was determined as being sufficient to test the diagnostic performance of cervical elasticity in mid trimester assuming that the risk of preterm delivery <34 weeks vs >34 weeks is 1:5 and that cervical elasticity area under curve (AUC) of the receiver operating characteristics (ROC) curve was 0.7, with 80% power and alpha of 5%. From the start of recruitment up to March 2018, only 15 (34.1%) out of 44 cases had completed all five serial cervix measurements. We aim to collect 120 completed set of measurements to allow our result to be statistically significant. Therefore, we increase the sample size to 200.

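### The Sample Size section gives no basis for 120 completed five-visit sets from 200 women: its only completion count implies about 68, and 120 would need 60% completion

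*Combined protocol and SAP*

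**What the plan says.** The Sample Size section first derives 120 women as "sufficient to test the diagnostic performance of cervical elasticity in mid trimester". The assumptions are an AUC of 0.7, a 1:5 ratio of births before to after 34 weeks, 80% power and 5% alpha.

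It then turns to completion of the visit schedule. "From the start of recruitment up to March 2018", it says, "only 15 (34.1%) out of 44 cases had completed all five serial cervix measurements". The next two sentences are "We aim to collect 120 completed set of measurements to allow our result to be statistically significant" and "Therefore, we increase the sample size to 200".

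The Methods section defines the schedule: "Measurements will be done at 5 visits: 11-15 weeks, 16-19 weeks, 20-23 weeks, 24-27 weeks, 28-32 weeks". It adds that how many visits a woman has depends on when she joins.

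The Main outcome measures section lists two outcomes: "The association of cervical consistency in mid trimester with spontaneous preterm birth in women carrying multiple pregnancies" and "The change in cervical consistency during pregnancy in women carrying multiple pregnancies".

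The Statistical Analysis section plans paired t or Wilcoxon signed-rank tests for changes in elastography. No section gives an expected completion rate, an inflation formula, the status of the 29 women without a full set, or a measure to raise completion.

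**The concern.** The figure of 200 is presented as the consequence of the completion count and the aim of 120 completed sets. A reader who applies the stated completion rate to 200 women does not get 120, and a reader who works back from 120 does not get 200.

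There is a second gap in the same lines. The 120 comes from an ROC calculation, which needs one mid-trimester measurement and a delivery outcome per woman. It is then counted in five-visit sets with no reason given.

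At stake are the stated yield of the study and the justification for its enrolment figure. The change of unit also leaves unclear which women count towards the 120.

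**Working it through.** **Inputs.** From Sample Size: 15 of 44 women complete; aim of 120 sets; enrolment of 200; AUC 0.7; ratio 1:5; risk of birth before 34 weeks about 20% (a 1:4 ratio); 80% power; 5% alpha. From Statistical Analysis: two-sided testing. Assumed, because the plan does not state it: null AUC of 0.5.

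**1. The plan's 120.** I used the Hanley-McNeil variance, with m births before 34 weeks, n others and A = 0.7:

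- Q₁ = A/(2 − A) = 0.7/1.3 = 0.538; Q₂ = 2A²/(1 + A) = 0.98/1.7 = 0.576.
- Alternative SE = √{[A(1 − A) + (m − 1)(Q₁ − A²) + (n − 1)(Q₂ − A²)]/(mn)}.
- Null SE = √{(m + n + 1)/(12mn)}.
- Power = Φ[(0.2 − 1.96 × null SE)/alternative SE].

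With m = 20 and n = 100, the null SE is 0.0710, the alternative SE is 0.0696 and power is 80.9%. In whole multiples of the 1:5 ratio, 20 + 100 = 120 is the smallest total reaching 80%. The 120 reproduces.

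**2. The plan's 200.**

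- Observed completion: 15/44 = 34.1%.
- Expected sets from 200 women: 200 × 15/44 = 68.2.
- Women needed for 120 sets: 120/(15/44) = 352.
- Completion needed for 120 sets from 200: 120/200 = 60%.

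The 200 does not reproduce by dividing by the completion rate. Multiplying instead gives 120 × (1 + 29/44) = 199.1, which rounds up to 200. That may be where the figure came from, but this is inference: the plan shows no formula, and the point does not depend on it.

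**3. What would rescue 200.** Two illustrations for the first 44 women:

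- If 12 of the 29 non-completers later finish, completion is 27/44 = 61.4% (11 would give 26/44 = 59.1%).
- If 19 of the 29 were not yet due and are left out of the denominator, it is 15/25 = 60%.

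Mixtures of the two would also do. The plan reports no figure for either.

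**4. Consequence for the ROC test.** The table uses the same formulas. The first power figure uses the null SE in the test; the second uses the alternative SE throughout.

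| Usable women | Ratio | m / n | Power |
|---|---|---|---|
| 120 | 1:5 | 20 / 100 | 80.9% / 81.9% |
| 120 | 1:4 | 24 / 96 | 86.3% / 87.5% |
| 200 | 1:5 | 33.3 / 166.7 | 95.7% / 96.0% |
| 200 | 1:4 | 40 / 160 | 97.7% / 98.0% |
| 68 | 1:5 | 11.3 / 56.7 | 56.2% / 57.8% |
| 68 | 1:4 | 13.6 / 54.4 | 62.5% / 64.5% |

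The rows for 68 apply only if the ROC analysis were limited to five-visit completers.

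**5. Consequence for the change outcome.** A paired test compares two visits, so a woman with both contributes whether or not she has all five. The plan has no power calculation for this outcome against which a shortfall could be measured.

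**The case against.** The strongest objection is that 15/44 is a snapshot taken during recruitment. The first and fifth windows are at least about 12 weeks apart, so some of the 29 women may simply not have been due. If 12 of them later finished, the 60% would be met, and nothing in the documents makes that implausible. This stands, and it limits the claim. For the same reason a confidence interval around 15/44 would not help: it would treat an interim count as an estimate of final completion.

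The objection does not remove the point. The plan offers no such adjustment, and not all non-completion is temporary: because the number of visits depends on when a woman joins, a late entrant can never supply five.

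A second objection is that no specified analysis is harmed. This also stands. The ROC test has ample power at about 200 usable women, and the paired tests need only two visits per comparison. What remains wrong is the stated yield and the reason given for 200.

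A reader might go further and infer one of two things:

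- **That the study will end with only 68 completed sets.** The documents do not show this, because the final status of the 29 women is not given.
- **That the main analysis is underpowered, at about 56-65%.** That would need the ROC analysis to be restricted to completers, which no section states.

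The opposite over-reading should be avoided too. The 96-98% assumes that all 200 women are usable and counts every birth before 34 weeks, whereas the first outcome concerns spontaneous preterm birth. As an illustration only, if such events were 10%, power would be about 84% at 200 women and 62% at 120.

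**Conclusion.** The point holds as a failure of derivation. The enrolment of 200 does not follow from the completion count and the aim that are given as its reason. The only rate stated implies about 68 sets against an aim of 120, and 120 would need 60% completion or 352 women. The completion arithmetic uses only the plan's own numbers.

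The conclusion is that the plan shows no basis for 120 sets, not that 120 is unattainable. The enrolment of 200 is defensible on another ground, the mid-trimester ROC test, given an AUC of 0.7, a null of 0.5, all births before 34 weeks as the endpoint, and enough women with a usable measurement and a delivery outcome. It should be corrected because a stated sample-size figure is wrong as derived and the correction is cheap.

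**What to change.** Keep the enrolment of 200 and replace the last two sentences of the Sample Size section with two statements.

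1. **Who counts towards the 120.** The 120 needed for the ROC analysis are women with an elastography measurement in one mid-trimester window, to be named by the investigators from the Methods schedule, and a known delivery outcome, whether or not they attended all five visits. Enrolling 200 gives 120 such women if at least 60% have both.
2. **Expected yield of completed sets.** Drop the aim of 120 completed sets and state the number expected from 200. Use the completion rate among all enrolled women whose fifth-visit window has passed, counting late entrants and women who delivered before that visit as non-completers. If that rate is not available, state that the interim 15/44 implies about 68 sets and may be an underestimate.

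The cost is rewording and a count from data already held, with no extra women. The downside is that the stated number of completed sets may become less favourable than 120.

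### The target of 120, sized for a mid-trimester test, is counted in women with all five scans, which leaves out births before the 28-32 week scan and late recruits

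*Combined protocol and SAP*

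**What the plan says.** The Sample Size section says that 120 women are "sufficient to test the diagnostic performance of cervical elasticity in mid trimester". It assumes an AUC of 0.7, a 1:5 ratio of births before to births after 34 weeks, 80% power and 5% alpha. This corresponds to the first main outcome: "The association of cervical consistency in mid trimester with spontaneous preterm birth in women carrying multiple pregnancies".

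The same section then reports that, up to March 2018, "only 15 (34.1%) out of 44 cases had completed all five serial cervix measurements". It continues: "We aim to collect 120 completed set of measurements to allow our result to be statistically significant". On that basis enrolment rises to 200.

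Methods sets the schedule: "Measurements will be done at 5 visits: 11-15 weeks, 16-19 weeks, 20-23 weeks, 24-27 weeks, 28-32 weeks". It adds: "The number of visits will be depended on when the subjects are initially recruited". On outcomes it says: "The delivery data and neonatal outcome will be collected from the medical notes and hospital electronic system", with no restriction to women who completed the scans.

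The Statistical Analysis section lists tests. It defines no analysis set, no rule for incomplete series and no index mid-trimester scan.

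**The concern.** The counting unit does not match the calculation. A test of mid-trimester elasticity needs one mid-trimester scan and a delivery outcome, whereas the recruitment target counts women with five scans. Two groups cannot reach five:

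- **Women who deliver before their 28-32 week scan.** All of them are births before 34 weeks, the endpoint used for sizing. Not all are spontaneous, so not every one is an event for the first main outcome.
- **Women recruited after 15 weeks.** They have missed the first window and can have at most four scans, even with a valid mid-trimester scan.

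Completion therefore depends partly on the outcome. If completers are the analysed sample, the earliest births drop out. The event rate and any predictive values then describe only women still undelivered at 28-32 weeks, which nobody knows when the mid-trimester scan is read. That fits poorly with the plan's stated purpose of finding women who would benefit from preventive treatment.

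**Working it through.** **Inputs from the plan.** AUC 0.7; 80% power; two-sided 5% alpha; births before 34 weeks given both as 1:5 (r = 1/6) and as about 20% (r = 0.20); 15 of 44 women with five scans; 200 to be enrolled.

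**Assumptions.** The null AUC is not stated; 0.5 is used. The share f of births before 34 weeks that precede the fifth scan is not in the documents; 10% to 50% is shown.

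**1. Reproduce 120.** With n1 events and n0 non-events, the Hanley-McNeil variance is

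V(A) = [A(1−A) + (n1−1)(Q1−A²) + (n0−1)(Q2−A²)] / (n1·n0), with Q1 = A/(2−A) and Q2 = 2A²/(1+A).

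Power = Φ{[0.2 − 1.96·√V(0.5)] / √V(0.7)}.

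For 20 + 100, √V(0.5) = 0.0710 and √V(0.7) = 0.0696, so power = Φ{(0.2 − 0.1392)/0.0696} = 80.9%. Twenty events is the smallest number that reaches 80% at 1:5, so 120 is reproduced exactly. At 20% risk (24 + 96) power is 86.3%.

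**2. Analyse 120 completers instead.** The event rate among women undelivered at the fifth scan is r(1−f)/(1−rf). Power uses the unrounded event count.

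| f | Events of 120, 1:5 | Power | Events of 120, 20% | Power |
|---|---|---|---|---|
| 10% | 18 | 78% | 22 | 84% |
| 20% | 17 | 74% | 20 | 81% |
| 30% | 15 | 70% | 18 | 77% |
| 50% | 11 | 58% | 13 | 66% |

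Power falls below 80% once f exceeds about 3% at 1:5, or about 23% at 20% risk.

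**3. Predictive values.** At 20% risk and f = 10-30%, the completer event rate is 18-15%. Take an illustrative cut-off with sensitivity = specificity = 0.645 (equal-variance binormal, AUC 0.70). PPV = 0.645p / [0.645p + 0.355(1−p)], which is 31% at p = 0.20 and 29-24% at the completer rates.

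**4. AUC.** A simulation used a proportional-hazards marker, Weibull delivery times (shape 10, 14 or 20), 20% risk, AUC 0.70, and a fifth scan uniform on 28-32 weeks. It gave f of about 34%, 22% and 12%, with a completer AUC of 0.69 to 0.70. No material AUC bias follows under this model.

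**5. How many women this involves.** Births before the fifth scan per 200 women = 200·r·f. For f = 10-30% this is 3.3 to 10 at 1:5 and 4 to 12 at 20%.

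**6. The five-scan count at the observed rate.** 15/44 = 34.1% (exact 95% CI 20.5-49.9%). 200 × 0.341 = 68 completers (41 to 100), with 56% power at 1:5 or 62% at 20%, before any loss to f.

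**7. The matching count.** Counted by mid-trimester scan, 80% power needs 118 women at 1:5 (117.3 rounded up) or 102 at 20% (101.5 rounded up). That is 59% or 51% of 200.

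**The case against.** The strongest reply is that the plan never restricts the mid-trimester analysis to completers. The first main outcome is framed for women with multiple pregnancies in general, Methods accepts women with fewer visits, and delivery data are collected for all. The five-scan sentence is a collection target, and it may serve the second main outcome, "The change in cervical consistency during pregnancy in women carrying multiple pregnancies", which does need serial scans. If all 200 had a usable mid-trimester scan, power would be about 96% at 1:5 or 98% at 20%. The term for a completed set is also undefined and could mean all visits due for that woman.

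Much of this stands. Selection on the outcome is a possibility, not something the plan prescribes, and the five-scan reading is the natural one rather than a formal definition. The AUC hardly moves, f is assumed, the plan names no PPV or cut-off, and 3-12 early births per 200 cannot explain most of the 29 non-completers among 44. The 68-completer figure is chiefly an enrolment shortfall, and it may be pessimistic because some of the 44 may still have been pregnant in March 2018.

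What does not stand is that the mismatch is therefore harmless. The plan ties statistical significance to completed sets, uses that count to justify 200, and offers only a mid-trimester calculation in support. The second outcome's need for serial scans does not make five scans the right unit for a number sized on the first.

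**Conclusion.** The concern holds. The counting rule contradicts the calculation that produced 120, and nothing else in the plan resolves which women enter the prediction analysis. There are two readings, and both need a correction:

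- **Completers analysed:** the sample is selected on the outcome. With f assumed at 10-30%, power for 120 completers is 78-70% at 1:5 or 84-77% at 20% risk, and predictive values apply to the wrong population.
- **All women with a mid-trimester scan analysed:** the selection disappears, but five-scan completion is the wrong basis for the increase to 200.

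The loss is moderate rather than severe: it depends on an undocumented f, and at 20% risk 80% power survives until f is about 23%. It should be fixed before the data are analysed, because the choice changes the event rate, the predictive values and the power.

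**What to change.** Define the analysis set for the first main outcome as every woman with a valid elasticity measurement in a named mid-trimester window and a known delivery outcome, whatever other scans she had. Count these women toward the 120. Keep five-scan completers as a sensitivity analysis.

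For the second main outcome, use all available scans, for example in a mixed model, and note that late-window measurements exist only for women still undelivered. Report how many women lacked the fifth scan because of delivery, late recruitment or a missed visit.

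The cost is rewording the Sample Size and Statistical Analysis sections, plus handling unbalanced serial data for the second outcome. No extra women or scans are needed, and delivery data are already to be collected without limiting them to completers.

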#### **Statistical Analysis:**

Changes in the cervical elastography will be compared using the Student paired two-tailed t test, and in the case of unequal standard deviation (SD), using a Wilcoxon signed-rank paired

two-tailed test. For comparison of frequencies, Chi-square test, or a two-sided Fisher exact test will be used where appropriate. Linear regression will be used to assess the correlations. Statistical analysis was performed using the Statistical Package for Social Science (SPSS) version 20.0 (SPSS, IL). The level of statistical significance is set at p<0.05 (two-sided).

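### Main outcome 2 (change in stiffness over five visits) has only a paired two-visit test at an unadjusted 5% level, with no overall test, named visit pair or adjustment; repeated across visits, it gives a false change in about 14–29% of studies

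*Combined protocol and SAP*

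**What the plan says.** - **Outcome.** Main outcome measures lists two items. The second is "The change in cervical consistency during pregnancy in women carrying multiple pregnancies".
- **Schedule.** Methods states: "Measurements will be done at 5 visits: 11-15 weeks, 16-19 weeks, 20-23 weeks, 24-27 weeks, 28-32 weeks". Sample Size adds: "We aim to collect 120 completed set of measurements to allow our result to be statistically significant". By a complete set it means all five serial measurements.
- **Test.** Statistical Analysis states: "Changes in the cervical elastography will be compared using the Student paired two-tailed t test". The fallback is described as "using a Wilcoxon signed-rank paired" testing. Either test compares two readings per woman.
- **Level.** The same section states: "The level of statistical significance is set at p<0.05 (two-sided". This single threshold covers every test in the plan.
- **Second condition.** Methods also has: "Women will be asked to perform Valsalva maneuvers and mesurements of cervical". That sentence goes on to include elastography. No section ranks the Valsalva reading against the resting one.

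The document contains no test across all five visits, no visit pair named as decisive, no list of pairs and no adjustment. Linear regression appears only for assessing correlations.

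**The concern.** A test of two readings cannot by itself answer a question about five visits. Either one pair is fixed in advance or the test is repeated. No pair is fixed, and choosing one after seeing the data carries the same inflation as testing them all.

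Five visits give four comparisons with the first visit, four adjacent comparisons, or 5 × 4 / 2 = 10 pairs. With each read at 0.05, the chance of reporting some change where none exists rises well above 5%. The point at stake is whether, and between which visits, stiffness changes. A wrong answer would be published as a finding on a main outcome.

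**Working it through.** **The plan's own figure.** The document states no error rate for main outcome 2 beyond 0.05 per test. Its one calculated figure concerns main outcome 1: "A sample size of 120 was determined as being sufficient to test the diagnostic performance of cervical elasticity in mid trimester". It reproduces. Take AUC 0.7 against 0.5 (the null value is assumed), a 1:5 ratio and hence 20 + 100 women. The Hanley–McNeil variance is [A(1−A) + (n1−1)(Q1−A²) + (n2−1)(Q2−A²)]/(n1·n2), with Q1 = A/(2−A) and Q2 = 2A²/(1+A). The standard errors are 0.0710 at A = 0.5 and 0.0696 at A = 0.7. Power is Φ[(0.2 − 1.96 × 0.0710)/0.0696] = Φ(0.874) ≈ 81%. So 120 is sound for the AUC, but it says nothing about change over visits.

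**Inputs for main outcome 2.** From the document: five visits, paired tests, 0.05 two-sided, 120 complete sets sought. Assumed, because the document is silent: which pairs are tested, normal data, and the correlation between visits. The main cases are equal correlation of 0.5 and first-order autoregressive correlation of 0.7. A random walk serves as an extreme of serial dependence.

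**No true change at any visit: chance of at least one p<0.05**

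| Pairs tested | Paired t, n=120: equal 0.5 / AR 0.7 | Large-sample limit: equal / AR 0.7 / random walk |
|---|---|---|
| One pair fixed in advance | 5% | 5% |
| Four against visit 1 | 15.8% / 14.0% | 15.6% / 13.7% / 12.6% |
| Four adjacent | 17.2% / 18.8% | 16.7% / 18.3% / 18.6% |
| All ten | 28.7% / 26.8% | 28.6% / 26.4% / 24.7% |

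The n=120 rates come from 6,000 simulated studies per setting. Their simulation error is about √(0.27 × 0.73/6000) ≈ 0.6 percentage points for the ten-pair row, so the columns agree. A separate run of 20,000 studies with equal correlation gave 15.9%, 16.4% and 28.8%. The ten-pair limit under equal correlation has an exact form: the chance that the range of five standard normals exceeds 1.96 × √2, which is 28.6%. At n=68 the ten-pair rates are 29.6% and 26.7%, so the inflation does not depend on reaching 120.

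**Change only at the last visit (1 SD lower).** The six pairs among the first four visits are true nulls.

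- Any p<0.05 among the six, either direction: 20.4% (equal) and 19.5% (AR 0.7) in simulation; 20.3%, 19.2% and 18.2% in the limit (equal, AR 0.7, random walk).
- A significant fall, that is, a false earlier softening: 11.7% and 10.3% in simulation; 11.6% and 10.1% in the limit.
- Either direction after Holm over all ten pairs: 4.5% and 4.2% in one run, 4.2% and 3.8% in another.

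**Cost in sensitivity.** The detectable change with 80% power, in SDs of the difference, is (z for the level + 0.842)/√n. The level is 0.05 unadjusted (z = 1.960). At Holm's strictest step it is 0.05/10 = 0.005 (z = 2.807).

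- n=120: 2.802/10.95 = 0.26; 3.649/10.95 = 0.33.
- n=68: 2.802/8.25 = 0.34; 3.649/8.25 = 0.44.

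The 68 is 200 × 15/44, the completion rate in Sample Size applied to the enlarged sample.

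**The case against.** Four objections have weight.

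1. **The plan does not say that it will test many pairs.** This stands. The paired test could be meant for a single first-to-last contrast, or for rest against Valsalva within a visit. A reader might infer that ten tests are planned and that the error rate simply is 29%. The document supports only the conditional statement. Treating the ten pairs as independent would give 1 − 0.95^10 = 40%, but that is wrong, because the pairs share visits.
2. **The plan promises no overall 5%.** This also stands. The level is set per test, the study is observational, the Hypothesis section concerns preterm birth, and main outcome 2 is worded descriptively. This is therefore a gap, not a contradiction. But the plan calls the outcome a main one, does not label it exploratory, and attaches a formal significance level.
3. **No change at any visit is an unrealistic null.** The late-change case answers this. A reader might take its roughly 20% as the chance of falsely claiming earlier softening. The tests are two-sided, and false softening alone is about 10–12%.
4. **A repeated-measures model would settle it.** Only in part: visit contrasts from a model, each read at 0.05, are inflated in the same way.

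A reader might also double the family for the Valsalva readings. The document does not say that they will be tested for change across visits, so the rates here leave them out.

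**Conclusion.** The concern holds as a gap in the analysis of main outcome 2. If the stated test is repeated over visits, the chance of at least one false change when there is none is about 14–16%, 16–19% or 27–29%, depending on which pairs are tested. Very strong serial correlation lowers the first and last ranges to about 13% and 25%. With change only at the last visit, a false earlier change in either direction arises in about 18–20% of studies. All these figures assume normal data and the stated correlations. None is a property of the plan itself, because the pairs are not specified. It deserves correction before the visit data are analysed; main outcome 1 is not affected.

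**What to change.** In Statistical Analysis:

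- Decide main outcome 2 on one overall test of visit at the 5% level (4 degrees of freedom) for the resting elastography reading. Take it from a mixed model for repeated measures with visit as a categorical factor and unstructured covariance, using all available visits.
- Report visit-to-visit comparisons with Holm-adjusted p-values over all ten pairs, and fix that family in the text so that it cannot be chosen later.
- Label the Valsalva readings secondary.

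An overall test on 4 degrees of freedom has no direction, so it should not be called two-sided.

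**Cost.** A few sentences and no new data. The smallest single-pair change detectable with 80% power rises from about 0.26 to at most 0.33 SD of the difference if 120 women contribute that pair, or from about 0.34 to at most 0.44 SD with 68. More than 68 may contribute to a given pair, since a pair needs only two visits. Using all available visits assumes that missed visits are missing at random given the observed readings, and the text should say so.

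### Unequal SD is no reason to leave the paired t-test, and a two-reading test loses precision for an outcome scanned at up to five visits

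*Combined protocol and SAP*

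**What the plan says.** Main outcome 2 in the combined protocol and SAP is "The change in cervical consistency during pregnancy in women carrying multiple pregnancies". Methods sets the schedule: "Measurements will be done at 5 visits: 11-15 weeks, 16-19 weeks, 20-23 weeks, 24-27 weeks, 28-32 weeks". It adds: "The number of visits will be depended on when the subjects are initially recruited". Partial series are therefore part of the design. Sample Size gives an interim count: "From the start of recruitment up to March 2018, only 15 (34.1%) out of 44 cases had completed all five serial cervix measurements". The same section aims for 120 complete sets from an enlarged sample of 200.

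For change, Statistical Analysis names one procedure: "Changes in the cervical elastography will be compared using the Student paired two-tailed t test". The alternative follows: "in the case of unequal standard deviation (SD), using a Wilcoxon signed-rank paired" test. Linear regression is named only for correlations. No repeated-measures model is named, and mean change is nowhere stated as the target.

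**The concern.** There are two separate problems.

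**Choice of test.** A single sample of differences has only one SD, so the unequal SDs must be those at the two readings. The paired t-test assumes nothing about their equality; that condition belongs to the comparison of independent groups. What matters is how the differences themselves are distributed, and the plan does not mention it. The signed-rank test tests mean change only if the differences are symmetric. Skewed readings whose spread differs between visits give asymmetric differences, so the rule can change the hypothesis in the very setting that triggers it.

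**Unused scans.** A paired test takes two readings at a time. A woman who entered after the first window, or missed a visit, adds nothing to a pair she lacks, although her other scans are correlated with the missing one and carry information about it.

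At stake are the interpretation and precision of one of two main outcomes. The study is observational and the obstetrician is blinded to the elastography, so the women's care is not affected.

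**Working it through.** **The plan's own figures.** 15/44 = 34.1%, as stated (exact 95% CI 20.5% to 49.9%). At that rate 200 women give 200 × 15/44 = 68 complete series; the target of 120 implies 120/200 = 60%. The sample size of 120 was set for main outcome 1. The documents give no power for main outcome 2, and no kPa distribution, SD, within-woman correlation or missingness pattern. All of these are assumed below.

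**1. The trigger.** With d = y₂ − y₁, the statistic is t = mean(d) / (s_d/√n), where Var(d) = σ₁² + σ₂² − 2ρσ₁σ₂. For SDs 8 and 16 and ρ = 0.5, Var(d) = 64 + 256 − 128 = 192. The sample SD of d estimates √192 directly, and σ₁ = σ₂ is needed nowhere.

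Simulated rejection at two-sided 5% with equal means (n = 68, 120, 200; ρ = 0.3, 0.5; 10,000 runs per cell):

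| Data | SD ratio | Paired t | Signed-rank |
|---|---|---|---|
| Normal | 1, 2, 4 | 4.5–5.4% | 4.7–5.3% |
| Lognormal | 1 | 4.6–5.1% | 4.5–5.2% |
| Lognormal | 1.5 | 4.9–5.5% | 7.4–23.0% |
| Lognormal | 2 | 5.2–6.5% | 11.6–58.9% |

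(Lognormal: mean 20 at both visits, first-visit CV 0.25 or 0.40.)

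What signed-rank detects can be shown for CV 0.40 and SD ratio 2. The log variances are ln(1 + 0.4²) = 0.148 and ln(1 + 0.8²) = 0.495. The medians are 20·exp(−0.148/2) = 18.6 and 20·exp(−0.495/2) = 15.6 kPa. The mean log change is −(0.495 − 0.148)/2 = −0.173. Its SD is 0.693 at ρ = 0.3 on the log scale and 0.610 at ρ = 0.5. The share of women who soften is Φ(0.173/0.693) = 60% and Φ(0.173/0.610) = 61%. The distribution shifts although the mean does not.

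**2. Precision.** For a contrast c between two visits, the pairwise variance is 2(1 − ρ)σ²/n_pair. The all-scans variance is c′[Σ N·p_k·V_k⁻¹]⁻¹c, summed over patterns k of attended visits, with V_k the covariance of the visits attended. Here N = 200, SDs are equal and the covariance is treated as known.

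*Worked case.* ρ = 0.3, 68.18 women complete, all others enter at visit 2, first-to-last change.
- Pairwise: 1.4/68.18 = 0.02053 (in σ²).
- All scans: regressing visit 1 on visits 2 to 5 gives slopes of 0.3/1.9 = 0.158 each and residual variance 1 − 0.36/1.9 = 0.8105. The variance is 0.8105/68.18 + 0.5895/200 = 0.01484, where 0.5895 is the variance of the remaining combination of visits 2 to 5.
- Ratio: 0.02053/0.01484 = 1.38.

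*Independent missingness.* Attendance per visit is (15/44)^(1/5) = 0.806, so any pair has 200 × 0.806² = 130 women.

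Variance ratios, pairwise to all scans, at 34.1% completion (ρ = 0.3 / 0.5):

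| Missingness | Visits 1–5 | Visits 3–4 | Visits 4–5 |
|---|---|---|---|
| Independent | 1.20 / 1.18 | 1.20 / 1.18 | 1.20 / 1.18 |
| Late entry, all at visit 2 | 1.38 / 1.36 | 1.00 / 1.00 | 1.00 / 1.00 |
| Late entry, even over 2–3 | 1.38 / 1.35 | 1.00 / 1.00 | 1.00 / 1.00 |
| Late entry, even over 2–4 | 1.37 / 1.34 | 1.09 / 1.08 | 1.00 / 1.00 |
| Late entry, even over 2–5 | 1.36 / 1.32 | 1.08 / 1.07 | 1.06 / 1.04 |

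Under late entry, visits 1–2 range from 1.15 to 1.38.

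At 60% completion, first-to-last is 1.08 to 1.09 (independent, 163 pairs) or 1.17 to 1.20 (late entry, 120 pairs). Over the confidence interval for completion it is 1.12 to 1.30 (independent) or 1.23 to 1.49 (late entry).

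**The case against.** The strongest reply is that signed-rank is not malfunctioning. In the skewed scenario the median falls and most women soften (54 to 61% across SD ratios 1.5 and 2), so the test is detecting a real shift. A reader might take rejection rates as high as 59% to be false positives for main outcome 2. The documents do not support that, because they never say that the outcome is mean change. What stands is narrower: the trigger has no basis, and a significant signed-rank result must not be read as a change in mean.

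A reader might also infer that partial series are discarded. They are not: a woman counts in every pair for which she has both scans. Only a complete-series analysis would drop her. The target of 120 complete sets may suggest one, but Statistical Analysis does not specify it.

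The loss of precision depends on the contrast, and the plan names none. It can be close to nil for later adjacent visits under late entry. The interim count may include pregnancies still in progress, so final completion may exceed 34.1%. None of this shows bias from pairwise testing, and a mixed model does not remove informative missingness either.

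The unnamed contrasts, the choice between resting and Valsalva readings, and multiplicity are missing detail. Unadjusted testing of all ten visit pairs would give a familywise error of about 28 to 29%, but the plan commits to no such set, so that figure does not support this point.

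**Conclusion.** The trigger is wrong as written. That follows from the definition of the paired t-test and needs no assumption; confidence is high. Its practical effect ranges from nothing (normal data, or equal SDs) to a change in the hypothesis tested (right skew with unequal SDs); the documents cannot say which applies.

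The mixed model is a cheap improvement rather than the repair of an invalid analysis. At 34.1% completion the pairwise standard error for first-to-last change is about 9% larger than with all scans under independent missingness (√1.18 to √1.20) and 15 to 18% larger under late entry (√1.32 to √1.38). At the implied 60% completion the gain is smaller. Confidence in its size is moderate, since correlation, equal SDs and missingness pattern are all assumed.

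**What to change.** Delete the unequal-SD trigger and state:

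> Change in resting elasticity (mean change, kPa) will be analysed with one linear mixed model on all available scans, with visit as a categorical fixed effect, a within-woman covariance that allows variance to differ by visit, and small-sample degrees of freedom. One global test of visit will be made at two-sided 5%, followed by Holm-adjusted visit contrasts. Scans missing because of early delivery may be informative, and this model does not remove that.

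A simulation check of this model (N = 200, 34.1% complete, unstructured covariance, Kenward-Roger degrees of freedom, 2,000 runs per setting) gave a global type I error of 4.9 to 6.2% with normal data and 5.7 to 6.8% with lognormal data, so it is slightly liberal under heavy skew.

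If paired tests are kept as support, use the paired t-test throughout for mean change. Do not choose between t and signed-rank by a check on the data. In the lognormal setting at SD ratio 2, a Shapiro-Wilk check followed by the chosen test rejected 10 to 56%, against 12 to 56% for signed-rank alone, so it protects hardly at all.

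The cost is a change of wording and slightly more analysis work. No new data are needed. The change should be made before the data are analysed.
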